When considering differences between SCI and uninjured controls, we found increased connectivity in the following networks: right amygdala to the left posterior temporal fusiform cortex ( $pFDR = 0.032$ ), left hippocampus to the right frontal pole ( $pFDR = 0.036$ ) the right occipital fusiform gyrus ( $pFDR = 0.025$ ), the right temporal occipital fusiform gyrus ( $pFDR = 0.036$ ), and the

left cerebellum 6 (pFDR =0.036). We also found significantly increased regional brain activity (ALFF) in the paracingulate gyrus (pFDR=0.004).

When considering differences based on the presence of neuropathic pain, we found decreased connectivity in the following networks: right thalamus to the left frontal operculum, (pFDR=0.0002) and left amygdala to the vermis of the cerebellum (pFDR=0.0001). We found increased connectivity in the left amygdala to cerebellum 3 (pFDR =0.0001).

We considering pain rating as a continuous variable, we found a significant positive linear correlation between pain rating and intrinsic connectivity of the post-central gyrus in the somatosensory area of the torso and lower body (pFDR =0.003). We also found a significant positive linear correlation between pain rating and brain activity (ALFF) in the periaqueductal gray area (pFDR=0.0009).

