
*Intervention Expectations.* This self-report will assess what participants expect their outcomes to be during and after their participation in the study.

*Study Expectancies.* Participants respond to 24 items about how they think they will function 7 weeks from now in areas such as pain, sleep, participation, work, social activities, and sexual functioning.

*Concurrent Pain Medication Use.* Although pain medications can confound the analgesic effects of brivaracetam, we consider it to be unethical to require participants to discontinue pharmacologic treatment for pain over the course of the study as a criterion for enrollment. In addition, to increase generalizability, it is important to recruit participants using pain medications. Therefore, we will record pain medication use over the course of the trial and consider this in the analysis.

*Pain Intensity and Medication Use Diary.* We will monitor daily pain reports and patient medication throughout the course of the study using a Pain Intensity and Medication Use Diary. Participants will be asked to record daily pain ratings (highest pain 0-10, lowest pain 0-10, and average pain 0-10) and any pain medication use. This diary will be started 1 week prior to drug treatment and maintained until completion of the study.

*Assessment of Brain Function with MRI.* All scans will be performed on the same scanner for this study. We will use the Siemens 3-T Prisma multi-band scanner. Prior to each scan, participants will be asked five questions regarding their pain now and over the last week as well as alcohol, caffeine, and tobacco use over the past 12 hours.

1. Structural MRI acquisition: We will acquire a T1-weighted Magnetization-Prepared Rapid Acquisition with Gradient Echo (MPRAGE) image [Repetition Time (TR)=2.5s, Echo Time (TE)=4.5ms, 0.8mm^3 voxels], and a T2 weighted Sampling Perfection with Application optimized Contrasts using different flip angle Evolution (SPACE) image [TR=3.2s, TE=565ms, 0.8mm^3 voxels]. We use special sequences for the scans to reduce the impact of head motion.

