2. Resting-state and task fMRI acquisition: The resting-state and task fMRI scans will be obtained with a T2\*-weighted multiband echo planar acquisition tipped 30 degrees relative to the Anterior Commissure - Posterior Commissure (AC-PC) plane as determined by the auto-align software. This acquisition protocol is designed to measure whole-head BOLD-contrast with optimal temporal and spatial resolution, and to reduce signal dropout [TR=0.8s; TE=37ms; Flip Angle=55°; 72 slices; multiband factor 8; 2mm isotropic resolution]. We will use the Framewise Integrated Real-time MRIMonitoring (FIRMM)

software to track head motion for each fMRI scan in real time. If visual inspection or FIRMM shows that image quality is substandard, the scan will be repeated immediately. After the MRI acquisition, a structured Quality Assurance (QA) process will occur within 72 hours to ensure that the data are of sufficient quality for subsequent analysis. Adhering to these QA procedures should result in over 95% usable data.

- i. Task 1: Mental body scan. Participants will be asked to focus with gentle, non-judgmental awareness on the sensations of the leg (that they experience having the most pain). In other words, they perform a gentle focused mental body scan and register any feelings of sensation in that limb. We alternate this task with rest periods. We chose Task 1 based on our previous study in adults with chronic low back pain showing OP1/OP4 and posterior parietal cortex activation after body awareness training during a similar task. Other brain imaging research showed that doing a mindful mental body scan significantly increases insula connectivity.
- ii. Task 2: Kinesthetic imagery of moving the limb. Participants will be asked to imagine the feeling of gently moving the painful leg (i.e., gentle non-judgmental awareness of any sensations during an imagined movement), alternated with rest. We chose this task based on tasks with mindfulness meditation showing insula and OP1/OP4 activation.

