- iii. Task 3: Whole-body movement task. Participants will perform a kinesthetic imagery of a whole-body movement, in which the hands are moving away and closer to the body symmetrically with guided breathing after viewing a video demonstration of the movement. We chose task 3 based on studies that demonstrate substantial spatial overlap of areas activated during motor imagery vs. motor execution. Our prior studies showed OP1/OP4 and posterior parietal cortex activation during this task in adults with chronic low back pain. We showed stronger insula connectivity after CMR in adults with SCI/D.
- iv. Task 4: Sensory stimulation task of the pads of the big toes and thumbs with a towel. Participants will not be made aware of when stroking occurs and will be asked after the scan if they sensed any hand or foot stimulation and, if so, where exactly they felt the stimulation.
- v. Task 5: Finger tapping. The participant is instructed verbally to tap their right fingers

MEDICAL PROTOCOL (HRP-590)

PROTOCOL TITLE: Brivaracetam to Reduce Neuropathic Pain in Chronic SCI: A Randomized, Double-Blind, Placebo-Controlled Clinical Trial

VERSION DATE: v7.0 APR2024

- vi. Task 6: Toe tapping. The participant is instructed verbally to tap their right foot. The task is alternated with rest.

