**Use of radiation: N/A**

**Use of Center for Magnetic Resonance Research:**

All participants who consent to MRI testing will get a 3T structural and functional MRI scan at Visit 2 and after completion of the 7-week treatment course (Visit 3). They will use the changing room to change into scrubs according to the CMRR protocol.

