Structural Preprocessing: We will perform preprocessing using the latest containerized fMRI preprocessing pipeline (FMRIPREP) version with standardized Brain Imaging Data Structure (BIDS) formatted Neuroimaging Informatics Technology Initiative (NIFTI) data. Each T1-weighted (T1w) volume will be corrected for intensity non-uniformity (INU) using N4BiasFieldCorrection and skull-stripped using antsBrainExtraction.sh (using the OASIS template). Brain surfaces will be reconstructed using recon-all from FreeSurfer, and the brain mask estimated will be refined with a custom variation of the method to reconcile Advanced Normalization Tools (ANTs)-derived and FreeSurfer-derived segmentations of the cortical gray-matter of Mindboggle. Spatial normalization to the International Consortium for Brain Mapping (ICBM) 152 Nonlinear Asymmetrical template will be performed through non-linear registration with the Registration tool of ANTs using brain-extracted versions of T1w volume and template.

fMRI Preprocessing: We will perform preprocessing with the latest

containerized FMRIPREP85 version with standardized BIDS formatted NIFTI data. Functional data will be slice time corrected using 3dTshift from Analysis of Functional NeuroImages (AFNI) and motion corrected using mcflirt. This is followed by co-registration to the corresponding T1w using boundary-based registration with 9 degrees of freedom, using bbrregister (FreeSurfer). Motion correcting transformations, field distortion correcting warp, BOLD-to-T1w transformation and T1w-to-template (Montreal Neurological Institute, MNI) warp will be concatenated and applied in a single step using antsApplyTransforms (ANTs v2.1.0) using Lanczos interpolation. Physiological noise regressors will be extracted by applying CompCor. Principal components will be estimated for the two CompCor variants: temporal (tCompCor) and anatomical (aCompCor). Framewise displacement and DVARS90 will be calculated for each functional run using the implementation of Nipype. Independent Component Analysis (ICA)-based Automatic Removal Of Motion Artifacts (AROMA) will be used to generate aggressive noise regressors and to create a variant of data that is non-aggressively denoised.

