#### Aim 2 statistical analysis

fMRI data will be processed using the conn functional connectivity toolbox with established standardized controls for multiple comparisons (SPM family wise error correction methods). Data will undergo realignment, scrubbing, artifact detection, and CompCor denoising. Primary analyses will focus on OP1/OP4 and insula regions-of-interest for resting-state connectivity and exploratory multivariate pattern analyses. Task-based fMRI will undergo the same preprocessing pipeline and will be modeled with a general linear model. Within-group pre-post changes in task-based brain activation and resting-state connectivity will be tested using paired t-tests or Wilcoxon signed-rank tests.

Between-group differences of pre-post changes in these measures will be tested using 2 sample t-tests or Mann-Whitney U tests. Mixed effects models with correlated errors will also be used to test the effect of CMR on brain imaging outcomes after adjusting for potential confounders, which will include the subject-level effect, time, group indicator, and time-by-group interaction as predictors, and age, race, and other covariates as appropriate. We will use False Discovery Rate (FDR) correction to control for the overall Type 1 errors for the voxel-level analyses. We will test the correlation between changes in brain function and clinical measures of sensory and

motor function using Pearson's correlations coefficients with 95% confidence interval calculated based on Fisher's Z transform.

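### fMRI Tasks 1 and 2 are aimed at the participant's most painful leg, and nothing keeps that leg the same from the pre-treatment scan to the post-treatment scan

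*Combined protocol and SAP*

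**What the plan says.** Section 5.0 (Assessment of Brain Function with MRI) lists six fMRI tasks. In Task 1 participants "focus with gentle, non-judgmental awareness on the sensations of the leg (that they experience having the most pain"; in Task 2 they "imagine the feeling of gently moving the painful leg". Neither names a side. Task 5 names the right fingers, and for Task 6 the text reads "The participant is instructed verbally to tap their right foot".

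The scan is done twice. Under Use of Center for Magnetic Resonance Research, consenting participants "will get a 3T structural and functional MRI scan at Visit 2 and after completion of the 7-week treatment course (Visit 3"), and Table 1 agrees. Before each scan "participants will be asked five questions regarding their pain now and over the last week", but no text links the answers to the choice of leg.

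Section 8.0 requires chronic sublesional neuropathic pain. It does not require that the pain be in a leg or on one side.

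For the analysis, Section 15.3 (Aim 2 statistical analysis) says "Within-group pre-post changes in task-based brain activation and resting-state connectivity will be tested using paired t-tests or Wilcoxon signed-rank tests". It adds two-sample tests of the change between arms, and mixed models with age, race and further covariates where appropriate. Task data are modelled with a general linear model. The OP1/OP4 and insula regions are named without a hemisphere, and the primary analyses on them concern resting-state connectivity. No image flipping, coding relative to the task leg, or side term is described.

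**The concern.** A pre-post contrast in task fMRI needs the same task at both scans. In Tasks 1 and 2 the target limb is defined by a symptom that the drug is meant to relieve. If the worse leg improves, the other leg may be the most painful at Visit 3. If leg pain resolves, Task 2 has no target. Either event happens after randomisation and can depend on treatment, so randomisation does not balance it between the arms.

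A second, smaller matter is pooling across people. Some participants will do the task for the left leg and others for the right. If the brain response follows the leg and the analysis is done by fixed hemisphere, pooling averages contralateral and ipsilateral responses.

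Task-based activity is a listed secondary outcome (Section 3.0), and parietal operculum activation is part of the Aim 2 working hypothesis (Section 1.1). Section 5.0 gives OP1/OP4 or insula involvement as the reason for choosing these two tasks.

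**Working it through.** **Text check.** Five things could settle the matter:

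- A named side: given for Tasks 5 and 6, absent for Tasks 1 and 2.
- A rule to record the Visit 2 leg and reuse it at Visit 3: absent.
- A rule for equal pain in both legs, no leg pain, or pain that has resolved or moved: absent.
- The hemisphere of the regions of interest: not stated.
- Side handling in the model: not named, though the covariate wording leaves room for it.

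The plan gives no effect size, SD or power for task fMRI, so there is no stated figure to reproduce. What follows is illustration on assumed inputs.

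**Pooling across people.** Take 20 per arm (Section 15.2), two-sided α = 0.05 and a normal approximation. The standardised effect giving 80% power when everyone uses the same leg is d = √(2/20) × (1.960 + 0.842) = 0.886. Let q be the share using the other leg and f the ipsilateral response as a fraction of the contralateral one. In an unaligned one-hemisphere region the average effect is d × m, with m = (1 − q) + q·f. Power is Φ(2.802·m − 1.960).

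| f | q = 0.3: m, power | q = 0.5: m, power |
|---|---|---|
| 0 | 0.70, 50% | 0.50, 29% |
| 0.5 | 0.85, 66% | 0.75, 56% |
| 0.8 | 0.94, 75% | 0.90, 71% |
| 1 | 1.00, 80% | 1.00, 80% |

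**Switching leg at Visit 3, with no drug effect on the brain.** Let A be baseline contralateral activation in SDs of change, so a switch moves a fixed-hemisphere region by g = (1 − f)·A in either direction. Let p be the share whose Visit 2 leg is contralateral to that region, and let s be the share switching in each arm, regardless of leg. The spurious arm difference is −(2p − 1) × g × (s_active − s_placebo).

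- p = 0.7, g = 1, switching 30% against 10%: −0.4 × 1 × 0.2 = −0.08 SD.
- p = 0.8, g = 1, switching 40% against 0%: −0.6 × 1 × 0.4 = −0.24 SD.
- p = 0.5: no mean shift. Switching adds variance s·g², for example 0.2 at s = 0.2 and g = 1.
- f = 1: g = 0, so no shift and no added variance.

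Simulating the first two cases (20,000 trials each, 15 scanned per arm, Welch t-test, nominal 5%) gives false-positive rates of about 5% and 9%.

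The two harms peak in different settings. Dilution is worst with legs split 50:50, where switching causes no mean shift. A mean shift needs most participants to share one worse leg, where dilution is smaller.

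**The case against.** The strongest reply is that the protocol is silent here and does not prescribe anything wrong. A reader might infer that the leg must be chosen afresh from the pain felt at Visit 3. The text does not say so, and site staff may reuse the same leg. That is right, and it limits the claim: re-selection is permitted, not required. Nothing prevents it either, and literal use of the instruction at Visit 3 leads to it.

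A reader might also infer that the plan contrasts left and right regions and so mixes hemispheres. It states no such contrast. A bilateral region would largely avoid the mixing, and a person who keeps the same leg has an unmixed pre-post change. The side-specific findings in Section 2.2, such as "right thalamus to the left frontal operculum", come from resting-state scans with no task leg. They do not show that responses to Tasks 1 and 2 follow the leg. This part of the reply stands.

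Recoding regions as contralateral or ipsilateral to the task leg also carries a risk. If the effect sits in a fixed hemisphere whichever leg is used, recoding causes the dilution itself: by symmetry with the f = 0, q = 0.5 case above, 80% power would become 29%.

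Finally, the reach is small: two of six tasks, in an optional scan, within an exploratory aim of a pilot trial. That lowers the priority but does not close the gap.

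**Conclusion.** The point holds in limited form. The limb for Tasks 1 and 2 is defined by the participant's pain, the scan is repeated after treatment, and nothing records or fixes the leg. The task can therefore change or become undefined between scans, possibly in relation to arm. Some participants may lack a defined task leg from the start.

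It would be tempting to conclude that the imaging comparison loses most of its power or carries a false-positive problem. The documents do not support that. The leg split, the switching rates, the degree of lateralisation and the number scanned are all assumed. Across the ranges shown, power goes from unchanged to 29%. The false-positive rate stays near nominal in the milder switching case and reaches about 9% only under extreme inputs. The firm harm is to interpretation: a change between two different tasks cannot be read as a treatment effect on one.

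Resting-state analyses, Tasks 3 to 6 and the pain endpoint are unaffected.

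**What to change.** In Section 5.0, Tasks 1 and 2: record at Visit 2 the leg used, use that same leg at Visit 3 whichever leg hurts more then, and pre-specify one rule for participants without a single worse leg. Table 1 places dispensing of study drug at Visit 2, so a leg fixed at that scan is chosen before treatment can influence it.

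In Section 15.3, Aim 2: state whether the OP1/OP4 and insula regions for Tasks 1 and 2 are bilateral or side-specific, and include the recorded task side as a covariate. The covariate absorbs a difference in mean change between left-leg and right-leg participants; it does not undo dilution. Coding regions as contralateral or ipsilateral to the task leg belongs in a sensitivity analysis, because it helps only if the response follows the leg.

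The cost is one recorded variable, one line in the scan script and a few sentences in the analysis plan, with no added scan time. For scans already done, the leg must be recovered from scan notes where possible and any switch flagged.

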**Table 1. Study Procedures**

Study Task	Screening	Visit 1 b	Visit 2 b	7-week intervention	Visit 3 c (end of study testing)	Visit 4 c
Screening Phone Survey	X					
Consent/randomization		X				
MRI Brain Scan (optional)			X		X	
Blood draw for biomarkers (optional)			X		X	
Physical health exam, health history screening		X			X	
Surveys		X			X	X c
Dispense study drug			X			
7-week drug intervention				X		
Limited safety labs (blood draw, required)	X a				X	
Pregnancy test (for women of child-bearing potential)					X	
Drug dose reduction protocol					X c	
Participant return remaining pills, bottle, and medication diary via mail					X c	
Adverse Events, PHQ-9, pain rating (highest, lowest, average)				Assessed weekly c		

PHQ-9: Patient Health Questionnaire 9-item

aMedical clearance must be clinically obtained from participants' primary care provider or other healthcare provider within 1 month prior to visit 1

bVisits 1 and 2 may be combined for participant convenience

cPerformed at the time of early withdrawal for those not completing the study

**Study drop criteria:** Participants will be removed from the study for safety reasons including drug intolerance, drug allergy, drug contraindications, development of depression, aggressive behavior, anxiety, or suicidality, or evidence of brivaracetam adverse events according to the manufacturer's prescribing guide (package insert). Poor drug compliance will be recorded for consideration during the analysis but will not be cause for removal from this study. In the case of drug intolerance, participants will reduce the drug dose under medical supervision of the PI until the drug can be safely discontinued.

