### **4.0 Study Intervention(s)/Investigational Agent(s)**

Description:

Intervention: brivaracetam or placebo administration. [name] (Co-I/study physician) currently holds an Investigational New Drug (IND) application for brivaracetam to treat severe neuropathic pain in individuals with SCI (IND # 150388). With regulatory support provided by UMN CTSI, we will submit this protocol to the FDA for review under the existing IND upon notification of funding. RxArtisans Pharmacy (Wayzata, MN) will FedEx the drug to the participant directly (study staff will send an email notification to the participant that the drug has been sent by overnight

mail) or to the designated contact at the enrolling site for distribution. To minimize wasting of drug, RxArtisans will dispense and ship prescriptions concurrent with the ramp-up schedule (weekly, biweekly, or as requested by study doctor). Participants will be asked to verify by phone or email receipt of study drug and initiation of the treatment course.

Drug dosage will be individually titrated for each participant with a goal of 100mg BID according to the following dose escalation protocol that we use clinically: 50mg BID for 1 week followed by 100mg BID for 28 days as tolerated. Participants will be allowed to reduce the dose of brivaracetam if they experience unacceptable side effects defined as increased somnolence according to routine clinical practice with other drugs in this class used for pain. Participants will be given an additional week to ramp up to 100mg BID, as needed. The 28-day treatment period might also be extended in the case of illness or other unanticipated event that impacts the ability to take the medication consistently. This will be determined on a case-by-case basis by the study team. The treatment course will be recorded and considered in analysis. A dose of 50mg BID or higher must be maintained to complete the trial. The study drug will be paid for by the study.

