## **12.0 Withdrawal of Participants**

Withdrawal Circumstances:

At any time after enrollment, a participant may be discontinued. Reasons for discontinuation of a participant from the study will include, but may not be limited to, the following:

- The participant is found to be intolerant to a required study procedure at any time point
- Failure of the participant to adhere to protocol requirements
- Positive hGC for individuals of childbearing potential
- The participant experiences a serious adverse experience at any time point
- The participant develops an inter-current illness that would, in the judgment of the investigator, affect assessments of clinical status to a significant degree.
- The participant enrolls in another investigational study
- The participant requests to withdraw from the study

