### **15.0 Statistical Considerations**

#### *15.1 Data Analysis Plan:*

For Aim 1, the first step for each outcome variable (e.g., pain,) is an unadjusted comparison across the groups as randomized. Each of the outcome variables uses a pre-defined instrument which has both top and bottom boundaries. These bounds are, however, wide enough so that the first steps will ignore the boundaries. The first analysis in each case is an unadjusted analysis and will be done in two ways: (1) a t-test (assuming unequal variances) and (2) a rank-sum test to take advantage of the Mann-Whitney score, which provides the probability that one group will have scores greater (less) than the other group. This statistic is the same as the c statistic widely used after logistic regression. The next step for each outcome is regression model with the main predictor being an indicator group. Standard covariates (e.g., demographics, and measures relevant to SCI such as severity and time since injury) will be included in the analysis. Robust estimator of the standard errors will be used. Predicted values will be checked to see whether any, and, if so, how many, are outside the boundaries of the measure used for that outcome. As a sensitivity analysis, regression models that recognize the boundaries will be used (e.g., fractional logistic regression or two-limit Tobit models). The main analysis will be Intention-to-Treat.

For Aim 2, we will use the same analytic approach we have refined in our 2 active rsfMRI studies and our ongoing task-based and rsfMRI study in adults with SCI and neuropathic pain.

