#### 18.2 Data Safety Monitoring

Plan for Monitoring Safety. The safety environment of UMN participants will be overseen and monitored by PI, [name], Co-I, [name], and Co-I/study physician, [name]. We will monitor to assure that participants meet eligibility criteria; that the informed consent process is conducted appropriately, that the data will be collected and analyzed as specified in the protocol, that adverse events (defined below) are reviewed promptly and reported as required (detailed below), that dropouts are documented, and that primary and secondary endpoints are evaluated. According to the data safety-monitoring plan, study participation will be terminated immediately in the event of injury or increased morbidity (drug intolerance). Data and all procedures will be monitored at each measurement time point and monthly throughout the duration of the study to ensure the safety of participants.

We will establish a Data Safety and Monitoring Board (DSMB) in accordance with NIDILRR and FDA guidance for clinical trial sponsors. UMN's institutional CTSI will assist with identifying board members and assist with managing board activities. The DSMB will review safety and efficacy data following a recruitment pause after the first 20 participants are enrolled and will make recommendations regarding continuation or termination of the study. The DSMB will also meet and review safety data quarterly and as needed throughout the duration of the study. The safety environment of all participants will be overseen and monitored by [name] (study Co-I). We will monitor to assure that participants meet eligibility criteria; that the informed consent process is conducted appropriately, that the data will be collected and analyzed as specified in the protocol, that adverse events are reviewed promptly and reported as required, that dropouts are documented, and that primary and secondary endpoints are evaluated. Data and all procedures will be monitored at each measurement time point and monthly throughout the duration of the study to ensure the safety of participants.

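### Participants removed for drug intolerance or adverse events have no primary pain rating planned at the Visit 3 time, and the intention-to-treat analysis does not say how their values enter

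*Combined protocol and SAP*

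**What the plan says.** The study drop criteria below Table 1 in Section 5.0 make removal mandatory: "Participants will be removed from the study for safety reasons including drug intolerance". They go on to name allergy, depression, aggressive behaviour, anxiety, suicidality and evidence of brivaracetam adverse events. Section 18.2 adds that "study participation will be terminated immediately in the event of injury or increased morbidity (drug intolerance"). Section 4.0 adds a further route to non-completion that is linked to tolerability: "A dose of 50mg BID or higher must be maintained to complete the trial".

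Footnote c of Table 1 is attached to the Visit 3 and Visit 4 columns, to the return of the medication diary and to the weekly row that includes pain ratings. It reads "Performed at the time of early withdrawal for those not completing the study".

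Section 15.1 plans a t-test, a rank-sum test and a regression model, and states "The main analysis will be Intention-to-Treat". It gives no missing-data method and no rule for values taken at early withdrawal. Its one named sensitivity analysis concerns the bounds of the scales. Section 12.0 (Termination Procedures) keeps and analyses data already collected unless the participant asks otherwise.

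On adherence, Section 5.0 says "Poor drug compliance will be recorded for consideration during the analysis but will not be cause for removal from this study". Section 12.0 lists "Failure of the participant to adhere to protocol requirements" among the reasons for discontinuation, under a permissive opening: "At any time after enrollment, a participant may be discontinued".

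**The concern.** An intention-to-treat comparison needs the outcome of every randomised participant at the same target time, whether or not the drug was still being taken. Here, stopping drug for intolerance or an adverse event also ends outcome collection, so the participants for whom the principle matters most lack the value it requires.

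The loss is unlikely to be unrelated to treatment. Depression, anxiety, aggressive behaviour, suicidality and drug intolerance appear both as removal reasons in Section 5.0 and as foreseeable drug risks in Section 13.0. If the analysis uses only those with a Visit 3 value, it compares people who tolerated active drug with people who stayed on placebo. That is a different question from the effect of assignment, and it concerns the primary endpoint. A rating that was never collected cannot be recovered at the analysis stage.

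**Working it through.** **1. What pain data exist for a removed participant**

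| Source | Where | Does it give the primary measure at the Visit 3 time? |
|---|---|---|
| International SCI Pain Data Set at early withdrawal | Section 5.0, Table 1 footnote c | No. The instrument asks about average pain over the last week, so it describes the days before removal |
| Weekly call ratings | Section 5.0 | No. They rate pain on the day of the call, and footnote c applies to this row |
| Daily diary | Section 5.0 | No. It runs until study completion, and footnote c places its return at early withdrawal |
| Retained data | Section 12.0 | No. This keeps what was collected and adds nothing later |

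So there are data, but none at the scheduled time, and no rule says which of them, if any, stands in for Visit 3.

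**2. The plan's attrition figures**

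Inputs (Section 10.0): 48 enrolled, 20% attrition, 40 completers. Allocation is 1:1 (Section 5.0), so 24 per arm. Check: 48 × (1 − 0.20) = 38.4, and 40 / (1 − 0.20) = 50. The stated 40 and 48 are each within two participants of these. Attrition is not split by arm or reason.

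**3. Size if stoppers are left out (illustration)**

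The target difference is 2 points (Section 15.2). Assume that 2.0 points is the effect among those who stay, that a fraction f of the active arm stops and is excluded, that stoppers benefit s points less than stayers, and that placebo participants who leave resemble those who stay. Then:

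- effect as randomised = 2.0 − f × s
- overstatement = f × s

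With no retained benefit (s = 2.0):

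| Active-arm loss f | Effect as randomised | Overstatement |
|---|---|---|
| 20% | 2.0 × 0.80 = 1.6 | 0.4 |
| 25% | 2.0 × 0.75 = 1.5 | 0.5 |
| 30% | 2.0 × 0.70 = 1.4 | 0.6 |

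The first row needs no imbalance between arms: 20% in each arm is the plan's own overall rate. Losses of 25% and 30% fit a 20% total if placebo loses 15% and 10%.

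In whole participants, 20% of 48 is about 10. If 5 of 24 are lost from the active arm, the overstatement is 0.208 × 1 = 0.2 points for s = 1 and 0.208 × 2 = 0.4 points for s = 2. If all 10 are lost from the active arm, the extreme case, it is 0.417 × 1 = 0.4 to 0.417 × 2 = 0.8 points.

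**4. If the early-withdrawal rating is used as the Visit 3 value**

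The formula above no longer applies. The rating may record a benefit still present on drug that is gone by Visit 3, or a partial course before any benefit has developed. The sign of the error cannot be derived from the documents.

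**5. Precision is not the issue**

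With 10 missing, the standard error is proportional to √(1/19 + 1/19) = 0.324 for an even split and √(1/14 + 1/24) = 0.336 if all are lost from the active arm, a difference of under 4%. The problem is bias.

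**6. Two passages to reconcile**

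Sections 5.0 and 12.0 differ on whether non-adherence can end participation. The Visit 3 description in Section 5.0 places it 5 weeks after Visit 2, while the paragraph on use of the magnetic resonance centre places it after completing a 7-week course. The scheduled Visit 3 time must be unambiguous before a rating can be required at it.

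**The case against.** The strongest reply is that the plan is silent rather than wrong. It compares groups as randomised, retains collected data and takes a full assessment at withdrawal. An analyst could therefore include every participant, and nothing prescribes a completer analysis; the 40 completers are an attrition allowance, not an analysis set. Section 4.0 also allows dose reduction and an extra ramp-up week, which may limit losses, and the trial calls itself a pilot.

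Much of this stands, and it rules out three stronger readings.

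- A reader might infer that pain will be missing altogether, and selectively from the active arm. Withdrawal-time, weekly and diary ratings exist. The drop criteria apply to both arms under masking, depression or anxiety can arise on placebo, and no arm-specific rates are given. Higher loss on active drug is a reasonable inference, not a stated fact.
- A reader might infer that poor drug compliance leads to removal. Section 5.0 says it does not; Section 12.0 is only permissive and refers to protocol requirements in general. That is a conflict in wording, not an established route of loss.
- A reader might take 2.0 / 1.4 = 1.43, a 43% overstatement, as the expected bias. It needs 30% active-arm loss, no retained benefit and complete exclusion together, and the documents supply none of these.

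What the reply does not remove is the missing Visit 3 rating. Including everyone by using an earlier rating still does not estimate the effect at Visit 3, and it leaves the choice of value open until the data are in.

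**Conclusion.** The point holds in this form: removal for intolerance or adverse events ends follow-up of the primary outcome at the scheduled time, and the analysis labelled intention-to-treat has no rule for the resulting early or missing values. If those participants are excluded, the effect is likely to be overstated. With no retained benefit, 2.0 points would stand for 1.6 to 1.4 points at 20% to 30% active-arm loss; with partial benefit the gap is smaller. If the early rating is substituted, the direction of error is unknown. The loss rates, the retained benefit and the exclusion are assumptions. The gap in follow-up and the silence of the analysis section are on the page. This is a cheap improvement, best made while Visit 3 ratings can still be collected.

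**What to change.** Leave the drug-stopping rules as they are.

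- In Sections 5.0, 12.0 and 18.2, distinguish stopping study drug from leaving the study. Anyone who stops drug and does not withdraw consent gives the International SCI Pain Data Set rating at the scheduled Visit 3 time, by phone or REDCap.
- In Section 15.1, analyse all randomised participants as assigned. Treat the early-withdrawal rating as auxiliary information, not as the Visit 3 value.
- Impute any remaining missing Visit 3 pain within arm from baseline and weekly ratings. Add a sensitivity analysis that gives active-arm dropouts placebo-like outcomes.
- Reconcile Sections 5.0 and 12.0 on non-adherence, and the two statements in Section 5.0 on the timing of Visit 3.

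The cost is a change of wording, a short rating for perhaps 10 of 48 participants and slightly more analysis. Weekly calls and fully remote participation are already in Section 5.0. The estimated effect may come out smaller than among those who stay on drug, but it will answer the question that the intention-to-treat label promises.
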